Hypothesis 1: Greater CB WML volume is associated with a) reduced resting-state connectivity of frontal, temporal, and cingulate regions and b) deficits in attention, memory and processing speed.

Hypothesis 2: Greater UF WML volume is associated with a) reduced resting state functional connectivity between frontocingulate and medial temporal regions, and b) greater depression severity and negativity bias.

Exploratory Hypothesis: Greater CB WML volume is associated with failure of anterior and posterior DMN nodes to deactivate during attentional components of the fMRI task. Greater UF WML volume is associated with greater medial temporal reactivity during affective components of the fMRI task.

Specific Aim 2: To determine whether deficits in tract structural / functional connectivity predict nonremission to antidepressant treatments and if these relationships vary based on antidepressant mechanism of action.

Hypothesis 3: Nonremission to escitalopram will be predicted by: a) greater WML volume in the CB and UF, and b) reduced resting functional connectivity between structures connected by the CB and UF. Greater WML severity and reduced functional connectivity in these tracts will not significantly predict response to placebo.

Hypothesis 4: Nonremission to bupropion will be predicted by a) greater WML volume in the UF but not CB, and b) reduced resting functional connectivity deficits between structures connected by the UF but not CB.

Exploratory Aims: **Expl. Aim 1)** To determine if specific cognitive measures may serve as markers of focal tract WML damage. **Expl. Aim 2)** To use whole-brain multimodal imaging approaches to examine how connectivity differences in other brain regions may also predict nonremission to antidepressants.

For exploratory analyses, we will also recruit 30 elders with no psychiatric history. Data from this population will help us understand whether our neural and cognitive findings in depression represent differences from what is seen in healthy aging, or whether our observations in depressed elders are within the range of normal aging. This will be important for data interpretation and planning for future projects.

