We will use a similar approach for Exploratory Aim 1, where we examine how cognitive test performance may serve as a marker of WML tract damage. Including the previous covariates plus education, cognitive test results will be on the independent side with tract WML values on the dependent side.

Data from nondepressed elders will be integrated into the above analyses. We will test for group differences in the neuroimaging and cognitive measures described above. We will also include a group variable (depressed or not depressed) in analyses.

Aim 2 examines how tract measures predict remission. Following our previous approach (21), our definition of remission is MADRS ≤ 7 . Secondly, we will examine drug response (50% improvement on MADRS). Remission / response status for subjects with missing data will be estimated via multiple imputation

method assuming that dropouts are missing at random.

We will use two regression models to test for mediation while adjusting for baseline MADRS, age, sex, and vascular risk. To assess indirect effects of tract WML and FC measures as mediator variables, we will regress a potential mediator on a tract-based measure (an explanatory variable of interest). We will fit another model in which antidepressant remission or nonremission serves as outcome variable, and the potential mediator and tract-derived measure serve as covariates. The second model can be either logistic or linear regression model depending on the nature of outcome. The product of two beta coefficients corresponding to the tract-based measure in the first model and to the mediation variable in the second model will be assessed by constructing bootstrapped 95% confidence intervals (CI); statistically significant difference from zero implies that the relationship between the outcome and explanatory variable is mediated by the variable in question (127,128).

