This approach will slightly differ for each study phase. For Phase 1, models will include drug arm (placebo or escitalopram). To examine for differences in how tract impairment affects remission in each arm, we will test for interactions between drug assignment and tract integrity (WML & FC). We will explore significant interactions in individual models. For subjects entering Phase 2, we will test for differences in tract integrity (WML & FC) between those originally assigned to escitalopram and placebo. If differences are observed, in models we will control for original Phase 1 cohort assignment. In exploratory models, we will use similar approaches to test for the additional effect of cognitive domain function (Table 5) on remission. We will also use this approach for Exploratory Aim 2 when we examine the effect of connectivity deficits in other tracts.

Importantly, the relationship between connectivity and antidepressant response may not be linear. It is possible that a ‘threshold’ must be crossed in order for tract connectivity deficits to influence response (3). To properly take into account nonlinear effect of a continuous predictor variable (e.g., WML, FC) on response variable (e.g., remission or nonremission) in the models, we will employ restricted cubic splines of the predictor. Statistical significance of the nonlinear terms via F-test implies that the relationship between the two measures of interest can be nonlinear.

15.1. Sample Size and Statistical Power:

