Aim 1: From our published report (129) correlations of the FC of the PFC with the amygdala and the hippocampus were in the range of 0.52 to 0.55. A sample of 130 subjects, will have > 90% statistical power for associations ≥ 0.30 (two-tailed $\alpha = 0.05$). However, our primary approach to the analysis of Aim 1 will use canonical correlation with no known powering algorithms; sample size and effect estimates are used to guide the appropriateness. Using the multiple regression approach (single dependent) as a conservative estimate, a sample size of 130 achieves 83% statistical power to detect an R^2 as small as 0.06 (standardized beta = 0.20, 6% shared variance) attributed to the association of WML with a significance level (alpha) of 0.05 after adjusting for other proposed covariates. These calculations assume that the variables for which we are adjusting have an R^2 of 0.10 (10%) (130). We suspect that the control variables will have a higher inter-correlation value, thus increasing our power for testing the effect of a single variable.

Aim 2: The study includes a placebo arm to identify effects specific to an active depressant while having a comparable number of subjects receiving each active drug. Powering the study for Phase 1, Table 2 presents estimates for our proposed sample size using unadjusted effects of low vs. high WML values on the respective

outcomes of interest found in our preliminary data. The logistic regression approach allows for the testing of effects adjusted for known covariates. Using this approach, assuming a base non-remittance rate of 0.36 (36%), a sample size of 130 will enable us to detect a log hazard ratio as small as 0.45 for a specific measure. We conservatively included an assumption that covariates would account to up to 10% share of the effect on nonremission. If that value is less, our statistical power will increase for the same hazard ratio. Using high vs. low tract WML volume as an example, after controlling for other effects, our sample will enable us to detect an effect on the likelihood of non-remittance of at least 25% (high WML vs. low WML, $0.45 / 0.36 = 1.25$ or 25% increase). Continuous as well as nonlinear operationalization of effects will be examined.

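### Section 15.1 gives Aim 2's logistic detectable effect as a log hazard ratio of 0.45; n = 130 has only about 16–18% two-sided power for the 25% high-versus-low increase claimed, and Aim 1's beta and R² disagree

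*Combined protocol and SAP*

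**What the plan says.** Section 15.1, Aim 2, introduces the adjusted analysis with "The logistic regression approach allows for the testing of effects adjusted for known covariates". Under that approach, with a base nonremission rate of 36% and up to a 10% share for covariates, it says that "a sample size of 130 will enable us to detect a log hazard ratio as small as 0.45 for a specific measure". No target power, alpha or sidedness accompanies this figure, and no unit for the measure. The text then takes high versus low tract WML volume as its example, divides 0.45 by 0.36 to get 1.25, and concludes that after adjustment the sample can "detect an effect on the likelihood of non-remittance of at least 25" percent.

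The analysis it supports is in Section 15.0. Remission is binary (MADRS 7 or below), and the models are logistic or linear, "adjusting for baseline MADRS, age, sex, and vascular risk". For Phase 1, "models will include drug arm (placebo or escitalopram"), and "we will test for interactions between drug assignment and tract integrity (WML & FC"). Hypothesis 3 in Section 2.0 expects tract measures to predict nonremission on escitalopram, while deficits "in these tracts will not significantly predict response to placebo". Section 9.1 allocates 2:1 in favour of escitalopram.

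For Aim 1, Section 15.1 gives 83% power for an R² of 0.06 with covariate R² 0.10, and describes that effect as "standardized beta = 0.20, 6% shared variance".

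**The concern.** Logistic regression estimates odds ratios, and the plan contains no time-to-event analysis of remission for which a hazard ratio would be the effect measure. The same 0.45 is first a log ratio and then, divided by 0.36, apparently a probability. A reader cannot tell which effect the sample was sized to detect, or with what power.

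This paragraph is the only sample-size support for the adjusted nonremission models; Table 2 covers unadjusted differences in MADRS means. If the trial finds no association, a reader who relies on the 25% claim could take that as evidence against an effect of that size, which the design has little chance of detecting. In Aim 1, a reader who relies on the beta rather than the R² would overestimate power by about 15 points.

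**Working it through.** **Inputs.** From Section 15.1: N = 130, nonremission 0.36, the 10% covariate share, and 0.45. Assumed: alpha 0.05 (for Aim 2 it is printed only over Table 2; two-tailed is stated only for the Aim 1 correlation); a 50/50 high/low split (none is stated for tract WML; Section 9.1 uses a pilot median for total WML); 0.36 as the low-WML rate, as the printed ratio implies; 0.45 per SD when the measure is continuous; and the 10% share read as predictor–covariate R², although the wording literally concerns the outcome.

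**1. The plan's own figure under the named model.** With no target power printed, a strict reproduction is impossible. For a log odds ratio b per SD, power = Φ(b·√[N(1−R²)p(1−p)] − z).

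- R² = 0.10: 0.45 × √(130 × 0.9 × 0.36 × 0.64) = 2.336. Power is Φ(2.336 − 1.96) = 65% two-sided and Φ(2.336 − 1.645) = 76% one-sided.
- No deduction: 0.45 × √(130 × 0.36 × 0.64) = 2.463. Power is 69% two-sided and 79% one-sided.
- The log odds ratio detectable with 80% power is 0.540 two-sided or 0.479 one-sided with R² = 0.10, and 0.512 or 0.454 without it. So 0.45 is close to an 80% effect only if the test is one-sided and the stated covariate allowance is dropped.
- Simulation (Wald test, R² = 0.10, two-sided) gives 61% with one covariate and 60% with the four named covariates plus drug arm.

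**2. The 25% claim.** For 65 per group, p̄ = 0.405 and d = 0.09:

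power = Φ{[d − z√(2p̄(1−p̄)/65)] / √[(0.36×0.64 + 0.45×0.55)/65]}

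- Two-sided: (0.09 − 1.96 × 0.0861)/0.0857 = −0.92, so 17.9%. One-sided: −0.60, so 27.4%.
- With the 10% allowance (58.5 per group): 16.5% and 25.6%.
- If 36% is the overall rate, the same ratio is 32% versus 40%, with 15.5% two-sided power.
- For 80% two-sided power: n per group = [1.96√(2 × 0.405 × 0.595) + 0.842√(0.36×0.64 + 0.45×0.55)]² / 0.09² = 466, or 932 in total.

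**3. Other readings of 0.45 as a high-versus-low effect (65 per group, unadjusted).** Both are larger effects than the 25% claimed.

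| Reading of 0.45 | Contrast | Relative increase | Two-sided | One-sided |
|---|---|---|---|---|
| Probability, as printed | 36% vs 45% | 25% | 18% | 27% |
| Log odds ratio | 36% vs 46.9% | 30% | 24% | 35% |
| Log hazard ratio, 1 − 0.64^exp(0.45) | 36% vs 50.3% | 40% | 38% | 50% |

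**4. What the logistic model can detect.** Simulated direct-effect model, Wald test, two-sided 0.05, 36% nonremission in both arms, R² = 0.10:

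- All 130: power at log odds ratio 0.58 per SD is 81% with one covariate and 80% with five. Detectable: about 0.58, OR exp(0.58) ≈ 1.8.
- Escitalopram only (130 × 2/3 ≈ 87): about 80% at 0.72 and 81% at 0.74. Detectable: about 0.73, OR ≈ 2.1.
- Drug-by-tract difference (87 vs 43, placebo slope 0): 79% at 1.25 and 81% at 1.30. Detectable: about 1.3 per SD.
- High versus low, 50/50: 36% vs 61% unadjusted (80.5%); 36% vs 62% adjusted (81%).

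With other nonremission rates, power at 0.58 for all 130 is 84.5% at 50%, 82.7% at 60% and 76.5% at 70%.

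**5. Aim 1.** Incremental R² = beta² × tolerance, and tolerance cannot exceed 1. A beta of 0.20 therefore gives at most 0.04. An R² of 0.06 needs a beta of at least √0.06 = 0.245 (0.258 at tolerance 0.9). Power comes from the noncentral F with f² = R²/(1 − R² − 0.10) and 3–6 covariates; the range spans noncentrality df × f² and N × f².

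- R² 0.06: f² = 0.0714, power 83–86%.
- R² 0.04: f² = 0.0465, power 66–68%.

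**The case against.** The strongest defence is that this is mainly a labelling slip. If 0.45 and 0.36 are two probabilities, the division is correct and only the words log hazard ratio are wrong. If 0.45 is a log odds ratio per SD, a one-sided test with no covariate deduction has 79% power, close to a conventional target. Both readings are possible, so it cannot be said that the division is necessarily invalid or that 0.45 is unattainable. Neither rescues the paragraph. The first leaves the 25% claim with under 20% two-sided power. The second requires dropping the covariate allowance that the plan says it included, assuming a sidedness and a unit that it does not state, and still gives no support to the high-versus-low claim.

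Three stronger readings are tempting but unsupported:

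- A reader might infer that the figure came from a Cox calculation, since Φ(0.45 × √(130 × 0.36 × 0.9) − 1.96) = 83%, the power printed for Aim 1. The documents do not say how it was obtained.
- A reader might quote up to 38% as the power for the 25% claim. That figure belongs to a 40% increase.
- A reader might conclude that the trial needs 932 participants. Section 15.1 does not establish 36% versus 45% as an effect that must be detected, and the Table 2 power figures are not in dispute.

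It is also fair that this is a correction to a power paragraph, and that simulated values should not enter a protocol without their assumptions.

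**Conclusion.** The point holds as a set of stated figures that the named model and sample do not deliver. Aim 2's detectable effect carries the wrong effect measure and no power, sidedness or unit. The printed 25% contrast has roughly one-fifth of the power usually sought, and under 30% even one-sided. This rests on the even split and alpha 0.05. The figures for 0.45 as a continuous effect rest also on the per-SD unit and, for the lower values, on the predictor–covariate reading of the 10% share.

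The Aim 1 inconsistency needs no design assumption, because beta squared caps the incremental R². Which of the two values was intended cannot be determined from the documents. The separate Aim 1 claim of over 90% power for a correlation of 0.30 is consistent with recalculation (94%). The defect should be fixed but is confined to Section 15.1.

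**What to change.** In Aim 2, delete the hazard-ratio wording and the sentence dividing 0.45 by 0.36. State the detectable effect as an odds ratio with its power, sidedness, unit and assumptions. For example:

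> By simulation of a direct-effect logistic model (Wald test, two-sided alpha 0.05, 80% power, 36% nonremission in both arms, predictor–covariate R² 0.10), 130 participants detect a log odds ratio of about 0.58 (OR about 1.8) per SD of a tract measure. The corresponding value for about 87 participants on escitalopram is about 0.73 (OR about 2.1) per SD. For the drug-by-tract interaction it is a log odds ratio difference of about 1.3 per SD, taking a placebo slope of 0. A 50/50 high-versus-low split detects about 36% versus 61% unadjusted and 62% adjusted. These figures do not apply to the bootstrapped mediation product.

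In Aim 1, either keep R² 0.06 at 83% and state the beta as at least 0.245, or keep beta 0.20 and restate R² as at most 0.04 and power as about 66–68%.

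This is rewording only, with no change to enrolment or analysis. The cost is a less favourable stated detectable effect.

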9.0. RANDOMIZATION & STUDY DRUG ADMINISTRATION

9.1. Randomization: After initial assessments, participants are randomized to double-blinded Phase 1 drug assignment (escitalopram or placebo). As our primary interest for Phase 1 is related to escitalopram response, we will allocate participants in a 2:1 drug-to-placebo ratio. Randomization will be conducted by the Vanderbilt Investigational Drug Service. Nondepressed individuals will not be randomized to study drug.

Randomization will be stratified by MRI measures of total cerebral WML volume. Our measurement of total WML volume is automated and available within 24 hours of the scan and subjects will be stratified as "high" or "low" total cerebral WML volume. Based on pilot data, we will use a cutoff of 3.86mL; this is the median 3T WML volume from a cohort of 145 depressed elders analyzed using our WML segmentation method. When we reach 50% enrollment, we will re-assess this cutoff based on study data and adjust if necessary.

If there are delays in scan processing, stratification will be determined using the Coffey-modified Fazekas visual rating scale (2), dichotomizing participants as "high" (2 or 3, confluence of foci) or "low" (0 or 1, absent or punctate foci).

MRI measures will only be used for stratification. They will not guide or determine treatment decisions.

9.2. Phase 1: Blinded Escitalopram or Placebo: We selected escitalopram due to its tolerability, ease of dosing, and lack of effects on dopamine and norepinephrine (115). The Vanderbilt IDS will prepare over-encapsulated escitalopram and matching placebo and maintain the blinded assignment in case of emergencies. Participants will receive one tablet (10mg or placebo) for at least 2 weeks. If tolerated, it can be increased to a target dose of two tablets (20mg) daily at the two-week study contact, but dosing changes will not be made at week 6 or later. For problems with tolerability, the dose can be reduced to the previous level, but not below one tablet daily.

9.3. Transition: After 8 weeks subjects will be assessed for remission (MADRS \leq 7). Those achieving remission will end their study participation. Those who are not remitted will have their Phase 1 drug tapered over a week to decrease the chance of discontinuation syndrome then progress to Phase 2.

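### The Aim 2 detectable effect of 0.45 with n = 130 assumes one tract effect shared by both Phase 1 arms, so it is too favourable for the escitalopram slope and for the drug-by-tract interaction

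*Combined protocol and SAP*

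**What the plan says.** Section 15.1 sizes Aim 2 for Phase 1 and states that "a sample size of 130 will enable us to detect a log hazard ratio as small as 0.45 for a specific measure". The inputs given are a base nonremission rate of 0.36 and an allowance that "covariates would account to up to 10% share of the effect on nonremission". The model named is logistic ("The logistic regression approach allows for the testing of effects adjusted for known covariates"), although the effect is called a log hazard ratio. No power is attached to 0.45.

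Section 4.0 makes 130 the evaluable depressed cohort, both arms together. Section 9.1 gives escitalopram response as the main Phase 1 interest and for that reason says "we will allocate participants in a 2:1 drug-to-placebo ratio". In section 2.0, Hypothesis 3 expects tract lesion volume and connectivity to predict nonremission on escitalopram, and adds: "Greater WML severity and reduced functional connectivity in these tracts will not significantly predict response to placebo".

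The Aim 2 analysis text in section 15.0 fits Phase 1 with both arms in one model containing an arm term, tests interactions between drug assignment and the tract measures, and uses individual models to explore significant interactions. Neither section 15.0 nor 15.1 gives a detectable effect for the escitalopram arm alone or for the interaction.

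**The concern.** A detectable effect computed on 130 people is the sensitivity for a slope to which all 130 contribute equally. Hypothesis 3 describes something else: a slope in about two thirds of them, and a weaker or absent one in the rest. Two quantities address that hypothesis, the slope among escitalopram recipients and the difference in slope between the arms. Both are estimated less precisely than a common slope in 130.

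The 0.45 is the only covariate-adjusted detectable effect the plan gives for remission. A null finding in the escitalopram arm, or a nonsignificant interaction, would be read against a sensitivity that the design does not have for either question.

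**Working it through.** **Inputs from the plan.** N = 130; effect 0.45; nonremission p = 0.36; covariate share R² = 0.10 (all section 15.1); 2:1 allocation (section 9.1), so 130 × 2/3 = 86.7, about 87 on escitalopram and 43 on placebo.

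**Assumptions.** Two-sided 0.05 (stated in 15.1 for Aim 1 only); effect per SD of a continuous tract measure; the same p and R² in both arms; no further dropout, since 130 is the evaluable number.

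**Formulas.** For a slope b in n people, power = Φ(b × sqrt(n × k) − 1.96), and the detectable slope at 80% power = (1.960 + 0.842) / sqrt(n × k), where
- Cox-type: k = p(1 − R²) = 0.36 × 0.90 = 0.324
- logistic: k = p(1 − p)(1 − R²) = 0.36 × 0.64 × 0.90 = 0.207

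**Reproducing the plan's figure (n = 130).**
- Cox-type: sqrt(130 × 0.324) = 6.490. At 83% power the detectable slope is (1.960 + 0.954) / 6.490 = 0.449, which matches 0.45. The 83% is borrowed from Aim 1 ("a sample size of 130 achieves 83% statistical power"); at 80% power the formula gives 0.432.
- Logistic: sqrt(130 × 0.207) = 5.192. Power for 0.45 is Φ(2.336 − 1.960) = 65%, and the detectable slope at 80% power is 0.540. The model named in the text does not reproduce 0.45.

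**Escitalopram arm (n = 87).**
- Cox-type: sqrt(87 × 0.324) = 5.309. Power for 0.45 is Φ(2.389 − 1.960) = 67%; detectable at 80% power, 2.802 / 5.309 = 0.53.
- Logistic: sqrt(87 × 0.207) = 4.247. Power for 0.45 is Φ(1.911 − 1.960) = 48%; detectable at 80% power, 2.802 / 4.247 = 0.66.

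**Drug-by-tract interaction (87 v 43).** The variance of a difference of two slopes is 1/(87k) + 1/(43k), so n is replaced by 87 × 43 / 130 = 28.8.
- Cox-type: sqrt(28.8 × 0.324) = 3.05. Power for a slope difference of 0.45 is Φ(1.374 − 1.960) = 28%; detectable at 80% power, 0.92.
- Logistic: sqrt(28.8 × 0.207) = 2.44. Power is Φ(1.099 − 1.960) = 19%; detectable at 80% power, 1.15.

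| Question | Power for 0.45, Cox-type / logistic | Detectable at 80% power, Cox-type / logistic |
|---|---|---|
| Common slope, n = 130 | 83% / 65% | 0.43 / 0.54 |
| Escitalopram slope, n = 87 | 67% / 48% | 0.53 / 0.66 |
| Interaction, 87 v 43 | 28% / 19% | 0.92 / 1.15 |

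**Sensitivity to the base rate.** The 36% is not tied to an arm. At n = 87 and 80% power, the Cox-type detectable slope is 0.448 if nonremission is 50% and 0.396 if it is 64%. The logistic value stays between 0.63 and 0.66 over 36% to 64%.

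**The case against.** The strongest reply is that 130 is the right number for the model the plan fits. Section 15.0 puts both arms in one Phase 1 model, and section 15.1 attaches 0.45 to a specific measure in Phase 1 without naming Hypothesis 3 or the escitalopram arm. That stands. A reader might infer that 130 is simply the wrong denominator, and the documents do not support this: the figure is valid for a tract effect common to both arms. What is missing is any figure for the arm-specific effect and for the interaction that the same section uses to compare arms.

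A reader might also take Hypothesis 3 to mean a zero slope on placebo. The pooled slope would then dilute to about 0.45 × 87/130 = 0.30, with about 49% power (Cox-type) or 34% (logistic) in all 130. Hypothesis 3 says only that prediction on placebo will not be significant, and a smaller non-zero slope in about 43 people fits that too. Those two percentages are a worst case, not the plan's assumption.

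The metric is also unsettled. The text names logistic regression, reports a log hazard ratio, and then divides 0.45 by 0.36 as though 0.45 were a rate. This is a separate defect. It is why both formulas are shown and why no single corrected value can be given until the sponsor states the metric and power. A higher nonremission rate would help under the Cox-type formula, but the plan assumes 36%.

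Table 2 does not fill the gap: it concerns unadjusted differences in mean MADRS, not remission.

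**Conclusion.** The point holds as a mismatch between the stated sensitivity and the question asked. The n = 130 figure applies to a tract effect equal in both arms, which is not what Hypothesis 3 expects. For the escitalopram slope, power for 0.45 is lower by about 16 to 17 percentage points (83% to 67% Cox-type, 65% to 48% logistic). For the interaction it is 28% or 19%. The percentages depend on the assumptions listed, on the 36% rate and, for the 83% starting point, on power borrowed from Aim 1. The direction depends only on the 2:1 split and on the effect differing between arms. The paragraph should be corrected; the design need not change.

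**What to change.** In section 15.1:
- State that the n = 130 figure assumes the same tract effect in both arms.
- State the power, and express the effect as a log odds ratio per SD to match the logistic analysis.
- Add the detectable effect for the escitalopram arm (n about 87): 0.66 at 80% power by logistic, or 0.53 if the Cox-type formula is kept.
- Add the detectable drug-by-tract interaction at 80% power: about 1.15 by logistic, or 0.92 Cox-type.

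Do not simply scale 0.45 by sqrt(130/87) = 1.22 and enter 0.55 as a log odds ratio per SD. By the logistic formula at n = 87 that value has Φ(0.55 × 4.247 − 1.960) = 65% power, so it would again be too favourable, and it says nothing about the interaction.

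The cost is a rewritten paragraph and a less favourable stated figure. No extra participants are needed.

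### The Aim 2 detectable effect of 0.45 has no stated power, does not reproduce under the named logistic method, and rests on a 10% covariate allowance whose description as conservative is unsupported

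*Combined protocol and SAP*

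**What the plan says.** Section 15.1, Aim 2, names logistic regression as the way to test covariate-adjusted effects. With a base non-remission rate of 0.36 it states that "a sample size of 130 will enable us to detect a log hazard ratio as small as 0.45 for a specific measure". The covariate allowance follows: "We conservatively included an assumption that covariates would account to up to 10% share of the effect on nonremission". Its direction is then given: "If that value is less, our statistical power will increase for the same hazard ratio". Neither the power nor the sidedness of the test is stated for this figure. The paragraph ends by dividing 0.45 by 0.36 to describe a 25% increase in non-remission for high against low tract WML.

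Section 15.0 describes the Aim 2 models as "adjusting for baseline MADRS, age, sex, and vascular risk". In the remission model, "the potential mediator and tract-derived measure serve as covariates". Drug arm and its interaction with tract integrity are added for Phase 1.

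**The concern.** The 0.45 is the only covariate-adjusted sizing for Aim 2, and so for Hypothesis 3 (tract WML and functional connectivity as predictors of non-remission to escitalopram). It is presented with a margin of safety. Two things do not fit.

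First, a detectable effect without a power is incomplete, and a logistic model does not produce a log hazard ratio. The figure may therefore have come from a formula that is not the planned analysis.

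Second, an allowance for which a smaller value gives more power behaves like the R-squared of the tested predictor on the other model terms. The model in section 15.0 includes several terms that the plan itself expects to be related to tract WML, so a ceiling of 10% needs justification before it can be called conservative.

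If the stated sensitivity is too favourable, a null tract or connectivity coefficient would be read as stronger evidence of no effect than it is.

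**Working it through.** **Inputs.** From section 15.1: n = 130, p = 0.36, B = 0.45, R² = 0.10. Assumed, because the Aim 2 paragraph does not say: two-sided alpha 0.05 (as stated for Aim 1), B as a log odds ratio per SD of the predictor, and 80% as conventional power.

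**Step 1: the plan's figure under the named method.** For logistic regression with a continuous predictor:

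λ = B·√[n·p(1−p)·(1−R²)], power ≈ Φ(λ − 1.960), detectable B at 80% = (1.960 + 0.842)/√[n·p(1−p)·(1−R²)].

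Here n·p(1−p) = 130 × 0.36 × 0.64 = 29.95.

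- R² = 0.10: √(29.95 × 0.90) = 5.192; λ = 0.45 × 5.192 = 2.336; power = Φ(0.376) = 65%; detectable B = 2.802/5.192 = 0.54.
- R² = 0: √29.95 = 5.473; λ = 2.463; power = 69%; detectable B = 0.51.
- Sample size for 80% power at B = 0.45 and R² = 0.10: 2.802²/(0.2304 × 0.2025 × 0.90) = 187.
- A one-sided test at R² = 0.10 gives about 75%, still short of 80%.

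So 0.45 is not reached at 80% power even with no overlap at all.

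**Step 2: where 0.45 may have come from.** An events-only hazard formula replaces p(1−p) by p: n·p = 46.8; √(46.8 × 0.90) = 6.490; λ = 2.920; power = Φ(0.960) = 83%; detectable B = 0.43. This fits the hazard-ratio label, but no time-to-event analysis of remission is planned.

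**Step 3: the 25% reading.** A rise in non-remission from 0.36 to 0.45 is a log odds ratio of ln(0.45/0.55) − ln(0.36/0.64) = 0.375, whereas exp(0.45) = 1.57. The paragraph thus uses 0.45 on two scales. Even as a per-SD effect at R² = 0.10, 0.375 gives λ = 0.375 × 5.192 = 1.95 and about 49% power.

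**Step 4: is 10% a conservative overlap?** Hypothesis 2 expects UF WML to be associated with functional connectivity and with depression severity. Connectivity (as mediator) and baseline MADRS both enter the outcome model. Section 15.1 uses 0.30 as the association that Aim 1 can detect with over 90% power. If UF WML had that correlation with each, and the two were roughly independent, R² = 0.30² + 0.30² = 0.18 before age and vascular risk are counted. The 0.30 is a planning value, not an estimate.

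**Step 5: sensitivity of the logistic figure to the overlap** (n = 130).

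| R² | Power at 0.45 | Detectable B, 80% power |
|---|---|---|
| 0.10 | 65% | 0.54 |
| 0.18 | 61% | 0.57 |
| 0.19 | 60% | 0.57 |
| 0.30 | 54% | 0.61 |

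**Step 6: can the documents fix the overlap?** In Table 2, baseline MADRS for right UF is 21.0 (12.2) for low and 29.5 (3.0) for high WML. With a fraction q in the high group, R² = q(1−q)·8.5² / [q(1−q)·8.5² + q·3.0² + (1−q)·12.2²].

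- q = 0.5: 18.06/(18.06 + 78.92) = 0.19.
- q = 0.2: 11.56/(11.56 + 120.87) = 0.09.
- The trial requires MADRS of at least 15. Truncating normal groups there (an assumption) moves the low group to about 27.3 (8.5) and leaves the high group unchanged. With equal groups R² is then about 0.03.

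The table gives no group sizes, so no single value follows.

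**The case against.** **Overlap is not what undoes 0.45.** This stands. Under the logistic formula the figure fails at 10% and at zero. Under the events-only formula, raising R² from 0.10 to 0.19 or 0.30 moves power only from 83% to 79% or 73%.

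**A reader might infer that the plan's own figures show an overlap of 19% to 30%.** They do not. The upper end would come from squaring the Aim 1 pilot values (0.52² = 0.27, 0.55² = 0.30), but the text says "correlations of the FC of the PFC with the amygdala and the hippocampus were in the range of 0.52 to 0.55", which is worded as connectivity between regions rather than tract WML with connectivity. The 19% is for right UF only, needs an equal split, and shrinks under the entry floor as shown. Table 2 has no baseline MADRS row for the CB.

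**The tract-plus-mediator model is tested by a bootstrapped product of coefficients, not by one coefficient.** Also fair. The higher overlaps matter only where tract and connectivity measures are fitted together, and section 15.1 does not say which model it sizes.

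**The 10% is worded as a share of the effect on the outcome, not as overlap among predictors.** True, so the overlap reading is an inference. It rests on the stated direction, by which a smaller share gives more power.

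**A reader might also call the Aim 1 remark an error:** "We suspect that the control variables will have a higher inter-correlation value, thus increasing our power for testing the effect of a single variable". It is correct if it means correlation of the covariates with the outcome. It is ambiguous, not shown to be wrong.

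**Conclusion.** The concern holds in a limited form. With B as a log odds ratio per SD and two-sided alpha 0.05, the Aim 2 sizing gives 65% power at 0.45 on the plan's own 10%, and the 80%-power detectable value is about 0.54. Because the plan states no power, the precise finding is that 0.45 is incomplete and does not reproduce at conventional power under the method named. It is consistent with a hazard formula that does not match the planned analysis.

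The description of 10% as conservative is unsupported, given the terms in the section 15.0 model and the plan's own hypotheses. That is weaker than saying that the overlap exceeds 10%: no document gives the R-squared of any tract measure on the other terms, and the true value could lie on either side. If it were 0.19 to 0.30, the detectable value would be about 0.57 to 0.61.

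**What to change.** In section 15.1, Aim 2:

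- Delete the word that calls the 10% assumption conservative.
- Define the R-squared as that of the tract (or connectivity) measure on all other terms in the fitted model, and say which section 15.0 model is being sized.
- Give the effect as a log odds ratio per SD, with alpha, sidedness and power, and bring the 25% sentence onto the same scale.
- Restate the 80%-power detectable value at n = 130 over an assumed range: about 0.54 (R-squared 0.10), 0.57 (0.19) and 0.61 (0.30). Label the higher values as sensitivity assumptions for models with tract and connectivity together, not as estimates.

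The cost is one recalculation and a few sentences. No extra patients are needed and no analysis changes. The stated sensitivity becomes less favourable, and null results should be interpreted against the restated values.
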